6.2 Intervention Planned Analyses

Analysis. All variables will be described using standard methods for continuous and discrete variables and examined for completeness. An interaction effect of discrimination and engagement in preventive care will be assessed, controlling for other confounders, using a logistic regression model with the binary

response (cancer screening). Additional analysis will be conducted, controlling for demographics, via a random intercept logistic regression model. Parameter significance will be determined at the 5% level.

Research measures collected at baseline, exit and 12 weeks post are: CRC knowledge, risk perception, medical mistrust, preventive health behaviors. At 12 week only, CRC screening or intent to screen, and participant satisfaction with the intervention will be asked. Process evaluation will assess any change in CRC knowledge, risk perception, medical mistrust, and preventive health behaviors at 12 weeks.

Feasibility will be assessed using a priori benchmarks for recruitment and retention. The recruitment benchmark will be consenting 100% of the recruitment goal. Acceptance rates and reasons for declining participation will be tracked. Information on refusals will be used to modify recruitment methods as needed. Retention benchmarks will be supported if $\geq 65\%$ complete both weeks 2 and 12 follow up. Engagement benchmarks will be supported if $\geq 65\%$ of intervention completers who do not have a primary care provider chose to receive navigation services; 80% of those consented view intervention materials (e.g., click on text/graphical data, view videos, complete risk assessment).

Preliminary Efficacy. A signal for efficacy will be considered positive if among those who complete the intervention a) most ($\geq 60\%$) complete CRC screening and b) $> 80\%$ acknowledge their intent to get screened.

Follow-up interviews. Interviews will be conducted with all participants to collect in-depth, descriptive feedback on satisfaction with the intervention content, delivery modalities, ease of use and usefulness. We will also interview clinic staff and Community Champions to gain insight into facilitators and barriers to recruitment efforts and response of the community to the intervention. Suggestions for additions and alterations will be solicited from all interviews.

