3.2 Hypothesis

H1.1. Lack of social support, higher medical mistrust, and perceived discrimination will be negatively associated with self-reported guideline concordant screening behaviors.

H2.2. Higher engagement in preventive care behaviors and greater perceived risk will be associated with higher completion of CRC screening. Subaim1a. Examine potential interactions between perceived discrimination, medical mistrust and engagement in preventive care behaviors.

H1.3. Increased perceptions of discrimination and greater medical mistrust will attenuate the relationship between preventive care and guideline concordant screening.

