6.1 Sample Size

The survey component was powered on the interaction term "discrimination*preventive care engagement", both continuous, using a simulation study of 1000 runs of a logistic regression model, with the binary screening behavior response (1 = screened, 0 = not screened). A sample size of 175 subjects generates 80% power to detect a "small to moderate" effect size of 0.38 (corresponding odds ratio = 2.01, using R package "effect size") for the interaction term (continuous*continuous), at 5% level of significance, using a one-sided Z-test. To account for individuals who start but do not complete the survey we have added a buffer of 20% which gives a sample size of n=210 for the survey.

We will also conduct focus groups with n=16 men.

Total project sample size n=226

Intervention Sample Size: To perform an initial test of efficacy, satisfaction and feasibility, we will test the intervention on 30 men.

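### The mistrust half of H1.3 has no planned test: Section 6.2 names only discrimination × preventive care, and omitting mistrust × preventive care can wrongly credit discrimination

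*Combined protocol and SAP*

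**What the plan says.** Section 3.2 sets out the Aim 1 hypotheses.

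- H1.1 covers three predictors: "Lack of social support, higher medical mistrust, and perceived discrimination will be negatively associated with self-reported guideline concordant screening behaviors".
- H1.2 (printed H2.2) covers two more: "Higher engagement in preventive care behaviors and greater perceived risk will be associated with higher completion of CRC screening".
- Subaim 1a asks for interactions among discrimination, mistrust and preventive care.
- The third hypothesis, H1.3, names two moderators: "Increased perceptions of discrimination and greater medical mistrust will attenuate the relationship between preventive care and guideline concordant screening".

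Section 6.2 gives the analysis: "An interaction effect of discrimination and engagement in preventive care will be assessed, controlling for other confounders". The model is a logistic regression for a yes/no screening outcome. A second model is then announced: "Additional analysis will be conducted, controlling for demographics, via a random intercept logistic regression model". Significance is at the 5% level, with sidedness not given.

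Section 6.2 is headed as the intervention analysis, but this sentence can only concern the Aim 1 survey. Discrimination is a survey measure in Section 5.8 and is absent from the intervention measures in Table 2.

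Section 6.1 powers the survey on the same single product term: "A sample size of 175 subjects generates 80% power to detect" an effect size of 0.38 (odds ratio 2.01), one-sided at 5%.

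**The concern.** H1.3 has two moderators and the analysis has one. Entering mistrust among the confounders gives it a main effect, which says nothing about whether it weakens the link between preventive care and screening. A survey meant to guide intervention content could therefore report on discrimination as a moderator and have no planned result for mistrust.

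The second risk is misattribution. Mistrust and discrimination may well be correlated in this population. If mistrust is the real moderator and its product term is left out, the discrimination product term absorbs part of its effect.

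The plan also names no model for H1.1 or H1.2 and does not mention centring. In a model with a product term on raw scores, the discrimination coefficient is its effect at a preventive-care score of zero. The care coefficient is its effect at a discrimination score of zero. Neither is the association that the hypotheses state.

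**Working it through.** **Hypotheses against planned terms**

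| Hypothesis (3.2) | Needs | Named in 6.1 or 6.2 |
|---|---|---|
| H1.3, discrimination | discrimination × care | yes, and powered |
| H1.3, mistrust | mistrust × care | no |
| H1.1, H1.2 | a stated model for each association | no |

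The omission follows from the text alone and needs no assumed figure.

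**The plan's own figures**

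- Effect size: d = ln(OR) × √3/π = 0.698 × 1.732/3.142 = 0.385 for OR 2.01. This agrees with the stated 0.38.
- Buffer: 175 × 1.2 = 210, as stated.
- Power: the 80% cannot be confirmed, because screening prevalence, main effects and score distributions are not given. With standardised, independent predictors, a log-odds coefficient of 0.38 gives 53–77% one-sided power across the settings tried, and 0.698 gives 92–99%. The stated 80% lies between these ranges. It is not evidence for or against the present point.

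**Misattribution**

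Assumptions: n=175; standardised scores; about 60% screened at the means; main effects of 0.3 log-odds per SD in the hypothesised directions; no true discrimination × care effect; a true mistrust × care effect of −0.38 or −0.698 per SD product, which are the plan's two figures with H1.3's sign; mistrust–discrimination correlation r.

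Write mistrust as r × discrimination plus an independent part. Mistrust × care then contains r × (discrimination × care). The single-interaction model therefore loads roughly r × (mistrust interaction) onto discrimination × care:

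- r=0.3: 0.3 × −0.38 = −0.114; 0.3 × −0.698 = −0.209
- r=0.5: 0.5 × −0.38 = −0.190; 0.5 × −0.698 = −0.349

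Simulated false rejection for discrimination × care, one-sided 5%, with mistrust in the model as a main effect only:

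| r | −0.38 to −0.698 |
|---|---|
| 0 | about 4% |
| 0.3 | about 13–25% |
| 0.5 | about 24–53% |
| 0.7 | about 40–79% |

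With mistrust × care also fitted, the rate returns to about 5%.

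**Cost in power of fitting both terms**

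Same setting, but with both interactions real and equal. Power for discrimination × care / mistrust × care:

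| r | −0.38 | −0.698 |
|---|---|---|
| 0 | 71% / 70% | 98% / 97% |
| 0.3 | 66% / 65% | 95% / 96% |
| 0.5 | 57% / 55% | 90% / 94% |
| 0.7 | 43% / 47% | 80% / 76% |

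If only discrimination × care is real (−0.38), adding the mistrust term lowers its power from 69% to 60% at r=0.5 and to 47% at r=0.7. Two independent tests at 5% have a family-wise error of 1 − 0.95² = 9.75%.

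**The case against.** The best defence is that the one test Section 6.2 does specify is sound in itself. Its product-term z-statistic is the same with raw or centred scores, and it holds its level if mistrust and discrimination are uncorrelated. Section 6.2 also plans a second, random intercept model, so it is not right to say that only one model is planned. Adding an interaction costs power and brings in a second test. The first and last of these points stand. The second model does not close the gap, because demographics are the only terms it names.

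A reader might go further and infer that the survey will report the wrong sign for discrimination under H1.1. The documents do not support that. Nowhere do they say that H1.1 or H1.2 will be read from raw-score coefficients, and silence on centring is not a plan to leave scores raw. The size of the problem also rests on an unstated quantity. Per SD, the raw discrimination coefficient equals (effect at mean care) − (interaction) × k, where k is the mean/SD ratio of the care score. With assumed values of −0.35 and −0.25, it turns positive only if k exceeds 0.35/0.25 = 1.4. In simulation, the wrong-sign rate runs from 11% at k=0.5 to 85% at k=5, and is about 1–2% when scores are centred. A positive interaction, which is how the printed odds ratio of 2.01 reads literally, would not reverse the discrimination sign at all.

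Nor is it fair to describe the difference between raw and centred coefficients as a loss of power for H1.1, since they estimate different quantities. What remains is a reason to state centring and name the model for H1.1 and H1.2.

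**Conclusion.** The point holds for the missing mistrust × preventive care term. That half of H1.3, and the matching part of Subaim 1a, has no planned test; this conclusion rests on the text alone. The misattribution risk is conditional. It requires that mistrust truly moderates, that discrimination does not, and that the two are correlated. Under those assumptions the false-positive rate for discrimination × care is about 13–25% at a correlation of 0.3 and 24–53% at 0.5, against a nominal 5%. For H1.1 and H1.2 the conclusion is limited to the absence of a stated model and centring rule; a reversed sign is not an expected result. The correction is worth making before analysis, and is proportionate to an observational survey aim.

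**What to change.** In Section 6.2:

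1. Mean-centre the scores. For H1.3 and Subaim 1a, fit discrimination × preventive care and mistrust × preventive care in the same logistic model and report simple slopes.
2. State that H1.1 and H1.2 (correcting the H2.2 label) are read from the centred terms or from a main-effects model. Either is acceptable; removing the product terms is optional.
3. Name up-to-date screening as the response for H1.1 and H1.3, which refer to guideline-concordant screening. Section 5.8 collects both ever-screened and up-to-date status, while Section 6.2 says only cancer screening. H1.2 speaks of completion of screening, so its response should be stated separately.
4. State the sidedness of the tests and how the two interaction tests are handled, for example by a multiplicity adjustment, or by declaring discrimination × care primary and mistrust × care secondary.

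In Section 6.1, say that the 80% power applies to discrimination × care in the single-interaction model, and that it will be lower with both terms if the moderators are correlated.

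No new data are needed, because medical mistrust is already a survey measure. The cost is revised wording, one more product term, a second test, and the power loss shown above.

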[figure not shown]

CLINICAL STUDY PROTOCOL

MCC-21-18632

SUCCEED: Engaging Black Men in CRC Screening

NCT05980182

9/08/2021

SUCCEED: Engaging Black Men in CRC Screening

Protocol Number

HM20023619

Principal Investigators

[name] (VCU)

[name] (VSU)

Protocol Version

8 September 2021

VCU Study Personnel

Principal Investigator	[name] Email: [contact]
Co-Investigator	
Research Assistant	
Student/RA	

Synopsis

Purpose

To determine the unmet needs, attitudes, barriers and facilitators of AA/Black men use of colorectal cancer screening and describe how community leaders such as barbers may act as Community Champions to educate and facilitate screening participation.

Objectives

Aim 1. Determine factors associated with self-reported CRC screening behaviors among (n=175) AA/Black men in Petersburg, VA.

Aim 2. Develop tailored S2S content for AA/Black men to be delivered using a combination of short video and text-based information optimized for delivery via QR codes for smartphones.

Aim 3. Test intervention on a sample of n=30 AA/Black men who are due for CRC screening. The primary aim is: completed CRC screening (any type) at 3months. Secondary aims are:

to collect process data to assess satisfaction and feasibility.

H1. Preliminary effectiveness of the intervention will be shown with >60% of men enrolled obtaining a CRC screen (any modality) by 12 weeks

H2. At Week 2 >80% of men enrolled will endorse an intention to be screened

H3. We will be able to recruit a sample of n=30 men into the intervention and maintain a retention rate (completion of baseline, 2 and 12 week surveys) >75%

Study Population

Survey Eligibility Criteria: Men aged 45-75 who reside in Petersburg and surrounding counties, and identify as AA/Black and have no personal history of cancer.

Intervention: For Aim 3 and additional criterion is that men have to be due for CRC screening upon study enrollment

Number of Participants

Survey: n=175

Intervention n=30

Study Design

Survey: Cross sectional; qualitative,

Intervention: single arm, pre-post Social behavioral intervention

Study Duration

Survey: 36 months total
 
Intervention: Aim 3: 12 months (once enrolled men are on study for three months)

Outcome Variables
 
Please see survey measures

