
Intervention: Aim 3:
 
Primary Outcome: CRC screening status at 3 months (>60%)
 
Secondary Outcomes:
 
• Intention to screen at 2 weeks (>80%)• Enrollment (target of n=30)• Maintain a retention rate (completion of baseline, 2 and 12 week surveys) >65% at 12 weeks• Viewing videos (# views, # repeat views)• Completion of baseline and follow up questionnaires (retention)• Responding to request to contact clinic/navigation services• Sharing any content with social network

Locations/Facilities
 
Surveys will be completed online
 
Recruitment for surveys will take place in-person, using social media, flyers in public spaces
 
Intervention: Aim 3: Recruitment will take place with flyers, word or mouth and presentations to introduce the study at partner and CAB member places of business and worship. These include community health clinics, local gyms, barbershops, stores, churches. We will use social media, newsletters and text messaging avenues of communication as utilized by our community and clinic partners. We will also use radio announcements on local health focused radio shows.

1 - Background/Literature Review

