5.3 Outcome Variables

Please see the survey measures

Aim 3:

Primary Outcome: CRC screening status at 3 months

Secondary Outcomes:

- Enrolment
- Viewing videos (# views, # repeat views)
- Completion of baseline, 2 week and 12 week questionnaires (retention)
- Completing values elicitation activity

- Responding to request to contact clinic/navigation services
- Sharing any content with social network

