One week after enrollment, men who have not engaged with the materials, completed the baseline questionnaire, or the navigation request will receive a text message aligned with the CRC risk perception and/or values elicitation that they shared with us at baseline. See table below.

Question: Which best describes your thoughts about colorectal cancer?

PARTICIPANT RESPONSE	AUTOMATED, TAILORED ANSWER
Never heard of it	Video # may interest you because it talk about CRC is and why screening can save your life!
Heard of it but not interested in screening	You might be interested to hear about the experiences of a CRC survivor. Video xx is “name” telling his story.
Heard of it and thinking about getting screened	You may want to check out video #, because it goes over the different types of screening options. The best one is the one that gets done!
Decided not to get screened	You might be interested to hear about the experiences of a CRC survivor. Video # is “name” telling his story. Video # also describes the many different screening options.
Decided to get screened	Inside the app there is a way to ask for a local clinic or screening navigator to call you directly. Check it out!
Have been screened in the past, but not recently	The best CRC screening test is the one that gets done! You may be interested in talking to a screening navigator. Inside there is a way to request a phone call from a local clinic.

Follow up: A three months after enrollment men will receive the final survey in their app and a text message notifying them that it is ready to be completed. Anyone who does not complete this survey within two weeks will be contacted by telephone by a study team member and given the option to complete it over the phone, have it emailed to them or to complete it in the app.

Table 2. Measures for intervention

Timing	CRC risk perception	Demographics	Health literacy (1 item)	Reg source of primary care	Health status	Intention to screen	Screen status	CRC knowledge	Medical mistrust
Baseline	X	x	x	x	x	x	x	x	x
2 weeks	X				x		x	x	
12 weeks	X				x	x	x		

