5.7 Data Collection

The survey will be a self-administered electronic survey (e-survey) expected to take 15-20 minutes to complete. Using a secure HIPAA compliant VCU Redcap survey housed on a VCU server, a unique survey link will be provided to interested participants (via email or QR code available on flyers and social media messaging).

Focus Groups: Participants (n=16) will be barbers employed at one of the four community partner barbershops. Two virtual focus groups of 6-8 barbers will be conducted. Focus groups will be conducted virtually using smartphone accessible VCU Zoom and will be video recorded, with permission. Participants will receive a \$20 honorarium for the 60-90-minute discussion.

Intervention: Baseline, 2 and 12 week follow up surveys will be collected on the app. If men do not respond to the follow up survey on the app they will be contacted by a study team member and provided alternatives for completion (see study procedures above).

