5.8 Data Collection Sources

Survey Measures. The survey has been designed to obtain key information while minimizing participant burden. *Demographics:* age, sex, highest attained education, annual household income, employment status, and marital status; health literacy (1 item); health status (1 item).

Medical Mistrust. measures (1) suspicion, (2) group (racial) disparities in health care, (3) lack of support from health care providers.

Perceived Racial Discrimination. Everyday Discrimination Scale reflect day-to-day experiences of unfair treatment. Higher scores corresponded to more frequent experiences of racial discrimination;

Preventive health care behaviors: The Good Health Practice Scale,⁶³ a 16-item scale that measures key preventive health behaviors. This scale has been shown to assess the avoidance of preventive health behaviors.

Social Support: MOS-SSS aims to assess the extent to which a person has the support of others to face stressful situations.

CRC Test fear and invasiveness and Cultural Attitudes about Masculinity: Males Role Norms Inventory-Short Form (MRNI-SF) is a 21-item questionnaire that assesses conformity to dominant cultural norms of masculinity (avoidance of femininity, negativity towards sexual minorities, self-reliance through mechanical skills, toughness, dominance, importance of sex, restrictive emotions). High total scores indicate greater conformity to traditional norms of masculinity

CRC Risk Perceptions. Lifetime risk of developing CRC will be asked on a 0-100% scale and a likert response adapted from the NIH HINTS.

Colorectal Cancer Screening Behaviors. Assessed using questions vetted by the national Behavioral Risk Factor Surveillance System we will measure those who have ever been screened and those who are up-to-date with screening

Focus Group: A focus group interview guide has been developed to inform how the barbers can be engaged to introduce the intervention, be empowered to have conversations about the need for CRC screening among Black men and encourage men to engage with the QR code and intervention materials.

Intervention.

1. Measures. See Table 2 above for all measures and timing of collection for the intervention.
 - a. Outcomes measures
 - i. CRC screening status (>60%) **OR**
 - ii. Intention to screen (>80%): from S2S
 - b. Covariates

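### H2 needs intention to screen at week 2, but neither schedule in the plan asks for it then; Table 2 and section 6.2 also conflict on three process measures

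*Combined protocol and SAP*

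**What the plan says.** **Intention to screen.** H2, in the synopsis objectives, reads "At Week 2 >80% of men enrolled will endorse an intention to be screened". The synopsis outcome list repeats this time point and threshold among the secondary outcomes.

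For timing, section 5.8 sends the reader to the table in section 5.4: "See Table 2 above for all measures and timing of collection for the intervention". That table marks intention at baseline and 12 weeks and leaves the 2-week cell blank. Section 6.2 gives its own schedule: "At 12 week only, CRC screening or intent to screen, and participant satisfaction with the intervention will be asked". A 2-week contact is planned, since section 5.7 states "Baseline, 2 and 12 week follow up surveys will be collected on the app".

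**Process measures.** Section 6.2 states "Research measures collected at baseline, exit and 12 weeks post are: CRC knowledge, risk perception, medical mistrust, preventive health behaviors", and then plans to assess change in those four measures at 12 weeks. Table 2 has CRC knowledge at baseline and 2 weeks, medical mistrust at baseline only, risk perception at all three visits, and no column for preventive health behaviors.

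**The concern.** H2 is one of three Aim 3 hypotheses and has a numerical success threshold. The same 80% intention figure is half of the efficacy signal in section 6.2. If the app surveys are built from either passage that schedules the item, H2 has no data at its own time point. The loss is permanent for each man once his second week is over.

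The week-12 item is a poor replacement. By then, men who have reached the primary outcome are already screened, so asking whether they intend to be screened means something different.

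The process-measure conflict is less serious. Those measures carry no hypothesis or threshold. Because Table 2 already has baseline knowledge and mistrust, that gap can be closed at any time up to the 12-week survey. Only baseline preventive health behaviors would be lost for good, and only if the baseline survey follows Table 2.

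**Working it through.** The plan gives no calculation to reproduce here. The check sets the passages side by side and counts men against the thresholds.

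**1. When is intention measured?**

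| Source | Time point for intention |
|---|---|
| Synopsis, H2 | week 2 |
| Synopsis, secondary outcomes | week 2 |
| Section 5.4, Table 2 | baseline, week 12 |
| Section 6.2, schedule sentence | week 12 only |
| Section 5.8, outcome measures | none given; refers to Table 2 |
| Section 6.2, efficacy criterion | none given |
| Section 5.3, secondary outcomes | intention not listed |

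Two statements require week 2, two schedules leave it out, and nothing reconciles them. Read literally, the 6.2 sentence also conflicts with Table 2 on two other points: Table 2 has intention at baseline, and screen status at baseline and 2 weeks.

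**2. Table 2, cell by cell.** There are nine measure columns, and each row has nine fields.

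- Baseline: 9 of 9 marked.
- 2 weeks: 4 of 9 (risk perception, health status, screen status, CRC knowledge).
- 12 weeks: 4 of 9 (risk perception, health status, intention, screen status).

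**3. What H2 needs.** With n = 30, 0.80 × 30 = 24, so exceeding 80% takes at least 25 men (25/30 = 83.3%). Week-2 intention responses available are 0 of 30 if the survey follows Table 2, and 0 of 30 if it follows 6.2.

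**4. Can week 12 stand in?** H1 requires more than 60% screened: 0.60 × 30 = 18, so at least 19 men (63.3%). If H1 is met, at most 30 − 19 = 11 men (36.7%) are still unscreened at week 12, against the 25 that H2 needs. This step assumes that intention is informative only in men not yet screened.

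**5. Process measures with a 12-week change planned in 6.2.**

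| Measure | Visits in Table 2 | 12-week change computable from Table 2? |
|---|---|---|
| Risk perception | baseline, 2, 12 weeks | yes |
| CRC knowledge | baseline, 2 weeks | no |
| Medical mistrust | baseline | no |
| Preventive health behaviors | no column | no |

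If Table 2 governs, 3 of 4 changes cannot be computed. If 6.2 governs, none is affected. Preventive health behaviors is also absent from the intervention measures listed in section 5.8. The *exit* visit in 6.2 is not defined, and section 5.7 lists only baseline, 2-week and 12-week surveys.

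**6. Sensitivity to table layout.** Columns can slip when a table is converted from PDF, so I kept the first mark in each follow-up row fixed and moved the others by one column.

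- Right: week 2 becomes risk perception, intention, knowledge and mistrust; week 12 becomes risk perception, intention, screen status and knowledge. Intention then falls at week 2, and the process conflict drops from 3 of 4 to 2 of 4.
- Left: intention again falls at week 2, but week 12 loses screen status, which is the primary outcome.

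Under either shift, the running text of 6.2 still contradicts H2 and the synopsis. Preventive health behaviors has no column under any alignment.

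**The case against.** The strongest reply is that the documents are split rather than silent. The synopsis puts intention at week 2 twice, a 2-week survey exists, and a study team could well include the item on that basis. The 0 of 30 is therefore conditional on building the survey from Table 2 or 6.2. That is correct, and the figure should be read that way. But section 5.8 names Table 2 as the source for timing, so following it is the natural course.

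A second reply is that the blank 2-week cell may be a layout artefact, and that Table 2 and 6.2 disagree with each other, so neither is a clean witness. The field counts match the header in every row, so a slip is only a possibility, and 6.2 contradicts H2 whatever the table shows. The clause in 6.2 might also be read as one either/or question at 12 weeks (screened or, if not, intending), but its restriction to that visit makes this strained, and it would still not supply a week-2 answer.

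Third, the comparison of 11 with 25 sets unscreened men against a threshold defined on all men enrolled. If screened men were counted as having intended screening, it would fail. This is fair: the comparison only illustrates why week 12 substitutes poorly, and the main point does not need it.

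Fourth, H2 is a secondary outcome in a 30-man pilot, and the primary outcome is scheduled at week 12 in both places. Sections 2.2 and 4.1 describe the intervention part as still awaiting submission or approval, which would leave time to correct the survey, although that wording may be out of date. These points limit the consequence; they do not remove the contradiction.

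**Conclusion.** The concern holds. H2 and a synopsis secondary outcome require intention at week 2, and both passages that schedule the item leave it out then. If either is followed, 0 of 30 men have the response for which H2 needs at least 25. Confidence is high because the contradiction between 6.2 and H2 is in running text and survives any reading of the table. It warrants correction before enrolment because the missing data cannot be recovered and the remedy is small. The primary outcome is not affected.

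The process-measure conflict is a separate, lower-severity point. That Table 2 and 6.2 contradict each other is clear. The count of 3 of 4 changes lost assumes that Table 2 governs and that its cells are placed as read; confidence in that count is moderate until the PDF layout is checked.

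**What to change.** - Add intention to screen to the 2-week row of Table 2 and to the 2-week app survey.
- Correct the 12-week-only sentence in section 6.2 so that the timing of intention and of screening status agrees with Table 2 and H2.
- Add week-2 intention to the secondary outcomes in section 5.3, to match the synopsis.
- Reconcile Table 2 with section 6.2 on process measures. Either add CRC knowledge and medical mistrust at 12 weeks and preventive health behaviors at baseline and 12 weeks, or remove from the planned change analysis any measure that will not be collected.
- Define the exit visit in 6.2 or replace it with a scheduled time point.
- Check the cell positions of Table 2 in the PDF while making these edits.

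The cost is one item in a survey that is already scheduled, plus text corrections. If the process measures are kept, the baseline and 12-week surveys gain a few items. Before enrolment this is a minor amendment with little added burden for participants.

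### Section 6.2 leaves open how already-screened men count on the intent criterion, and one natural scoring makes its two efficacy criteria mutually exclusive

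*Combined protocol and SAP*

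**What the plan says.** The decision rule is in section 6.2, under Preliminary Efficacy. It opens "A signal for efficacy will be considered positive if among those who complete the intervention a) most", sets the screening threshold at 60% or more, and adds with *and* that more than 80% must "acknowledge their intent to get screened". One denominator governs both parts. The rule gives no visit for the intent part and does not mention men who have already been screened.

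Earlier in the same section the timing is given: "At 12 week only, CRC screening or intent to screen, and participant satisfaction with the intervention will be asked".

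Other places treat intent differently:

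- Synopsis, Objectives, H2: "At Week 2 >80% of men enrolled will endorse an intention to be screened". The synopsis list of secondary outcomes also puts the 80% target at 2 weeks.
- Synopsis, Objectives, H1 judges screening alone: "Preliminary effectiveness of the intervention will be shown with >60% of men enrolled obtaining a CRC screen (any modality) by 12 weeks".
- Section 5.4, Table 2, as extracted, marks intention at baseline and 12 weeks but not at 2 weeks, and marks screening status at all three. The cell alignment may have suffered in extraction.
- Section 5.8 lists the screening outcome and then "Intention to screen (>80%): from S2S", joined by a bold *OR*, with no visit given and no item wording.

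**The concern.** Every man enters Aim 3 due for screening, so a screen during follow-up is the act that fulfils the intention. If both are recorded at the same 12-week visit and both thresholds apply to the same men, success on screening shrinks the group who can still say that they intend to be screened. Under that scoring, the better the intervention does on its primary outcome, the worse it does on the second criterion.

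This is the only efficacy decision rule in section 6.2, for a single-arm pilot with no control group and no formal test. If the scoring is settled only after the results are known, the choice can decide whether the signal is reported as positive.

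**Working it through.** The plan gives no calculation for the 60% and 80% thresholds or for n=30, so there is no stated figure to reproduce. The check is integer counting.

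**Inputs.** Criterion (a) is at least 60% screened and criterion (b) is more than 80% intending (section 6.2). The sample is 30 men (section 6.1). Section 6.2 does not define completing the intervention. I therefore take the number of completers, n, as 30, or as the smallest number meeting each retention target: more than 75% in H3 (0.75 × 30 = 22.5, so 23) and at least 65% in section 6.2 (0.65 × 30 = 19.5, so 20).

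**Step 1: intent at 12 weeks, screened men scored as not intending.** Men needed for (a) = 0.60n rounded up. Men needed for (b) = the smallest whole number above 0.80n. Most who can intend once (a) is met = n minus the number needed for (a).

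| n | (a) needs | (b) needs | Most who can intend | Share |
|---|---|---|---|---|
| 30 | 18 | 25 | 12 | 40.0% |
| 23 | 14 | 19 | 9 | 39.1% |
| 20 | 12 | 17 | 8 | 40.0% |

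At n=30, meeting both would need 18 + 25 − 30 = 13 men counted as both screened and intending. Conversely, meeting (b) allows at most 30 − 25 = 5 screened (5/30 = 16.7%). For any n, the ceiling on intent is 1 − 0.60 = 0.40, below 0.80.

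**Step 2: the other readings, at n=30 with 18 screened.**

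- Screened or intending both count: 25 − 18 = 7 of the 12 unscreened men must intend. Reachable.
- Intent assessed among unscreened men only: more than 0.80 × 12 = 9.6, so 10 of 12. Reachable.
- Intent taken at Week 2: a man can intend at Week 2 and be screened by Week 12, so the ceiling in step 1 does not apply. Only men screened in the first two weeks raise the scoring question, and up to 5 of 30 could be scored as not intending without missing 25. Reachable.

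**Step 3: one data set, two answers.** Suppose 18 of 30 are screened by 12 weeks and all 12 others intend to be. Criterion (a) is met at 18/30 = 60%. Criterion (b) is 12/30 = 40% (fail) if screened men count as not intending, and 30/30 = 100% (pass) if they count towards it.

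**Step 4: can the Week 2 reading be carried out?** Section 6.2 asks screening or intent at 12 weeks only, and Table 2 as extracted has no intention mark at 2 weeks. Under that schedule the data for H2 would not exist.

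**The case against.** A reader might infer that the joint signal can never be positive, or that the two criteria oppose each other under any common denominator. The documents do not support either. Criterion (b) does not say that a man must still intend to be screened at 12 weeks, and nothing says that a screened man is a non-intender. The phrase joining screening and intent with *or* in the 12-week sentence can be read as one item on which either answer counts. The intention item itself is not shown, so a screened man might truthfully answer yes about future screening. The only explicit time point attached to the 80% figure is Week 2, where the ceiling disappears. Of the four readings checked, one is impossible and three can be met.

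Nor does it follow that a successful pilot must be declared negative. H1 rests on screening alone, intention is a secondary outcome, and if the *OR* in section 5.8 means that either target suffices, meeting the screening target would be enough. No go/no-go decision is tied to the joint signal.

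These points limit the conclusion but do not remove the defect. Each reachable reading departs from a term of section 6.2 or fills a gap in it. The composite goes beyond the wording of (b), and Table 2 lists intention and screening status as separate measures. Restricting (b) to unscreened men changes the stated denominator. Taking intent at Week 2 conflicts with the 12-week-only sentence. Settling *and* versus *OR* would still leave screened men unscored on intent.

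Men screened within the first two weeks could also count against H2, but that effect is minor: five such men can be absorbed, and the plan gives no early screening rate.

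**Conclusion.** The point holds as a conditional conflict and a gap in definition. If intent is taken at 12 weeks among all completers and screened men are scored as not intending, the section 6.2 rule cannot be met: at most 40% against more than 80% required. The plan neither adopts nor excludes that scoring, and the choice can move criterion (b) from 40% to 100% on the same 30 men. Separately, the time point for the 80% target is contradictory, and the schedule in section 6.2 cannot supply the Week 2 data that H2 needs. That second conclusion rests mainly on the section 6.2 text, with Table 2 as support subject to its extraction.

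Severity is moderate: the primary outcome is judged on its own under H1, but the only efficacy rule in section 6.2 cannot be applied without a decision that the plan leaves unmade.

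**What to change.** 1. State one time point for the 80% intent criterion and collect intention at that visit. Bring the synopsis (H2 and the secondary outcomes), Table 2 in section 5.4 and the 12-week-only sentence in section 6.2 into line with it.
2. Define criterion (b) as screened since enrolment or intending to be screened, over the same denominator as (a). Ask the intention item only of men who report no screen since enrolment. Report intention among still-unscreened men descriptively.
3. Reconcile *and* in section 6.2 with *OR* in section 5.8. In the same edit, settle completers (6.2) versus men enrolled (H1 and H2), and at least 60% versus more than 60% (18 versus 19 of 30).

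The cost is protocol wording and one skip rule in the app survey, plus an added intention item if Week 2 is chosen. The downside is that, at 12 weeks, the composite overlaps with (a) and is a less demanding second test: with 18 of 30 screened it needs only 7 of the 12 unscreened men to intend. The plan should say so.
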